**Statistical Analysis Plan**

Catalyst Biosciences, Inc. Protocol # MAA-201

Version 2.0

Syneos Health #1009647

- Incidence of TEAE by relationship to study drug (related, not related). Missing relationship will be considered as related.
- Incidence of serious TEAEs
- Incidence of serious TEAEs related to study drug
- Incidence of TEAEs leading to study drug withdrawn

All AEs will be listed.

## 12.4 LABORATORY EVALUATIONS

All clinical laboratory parameters will be converted to consistent units according to the International System of Units (SI) before summarization.

Laboratory data will be summarized by the type of laboratory test. Normal reference ranges and abnormal results will be used in the summary of laboratory data. Data will be flagged according to the reference limits (high or low) if applicable.

Descriptive statistics will be calculated for each numeric laboratory test parameter by study part / visit and dose level for actual values and changes from baseline. In addition, change from baseline to the last assessment of the final dose level will be summarized. For chemistry and hematology lab tests, shift tables showing baseline and post-baseline visit will be performed for the categories low, normal, and high. Additionally, the shift from the study baseline to the final value in each dose level will be provided.

## 12.5 VITAL SIGNS

Descriptive summaries of actual values and changes from study baseline will be calculated for vital signs by study part, dose level and each visit, which includes blood pressure (BP), heart rate (HR), respiration rate (RR), body temperature, weight and BMI. In addition, change from baseline to the last assessment of the final dose level will be summarized.

Vital sign results for each parameter will then be tabulated for actual and change from period baseline values by study part, dose level and each visit.

The same method of calculating BMI in [section 7.2](#) will be used;

All vital sign data will be listed by subject and time of measurement.

## 12.6 ELECTROCARDIOGRAM (ECG)

A standard 12-lead ECG will be performed at the visits outlined in [section 3.8](#). All ECGs should be assessed by the Investigator and deemed “Normal”, “Abnormal, not clinically significant” and “Abnormal, clinically significant”. A shift table showing baseline to

**Statistical Analysis Plan**

Catalyst Biosciences, Inc. Protocol # MAA-201

**Version 2.0**

**Syneos Health #1009647**

post-baseline by study part and visits /dose level will be performed for the above categories. Additionally, the shift from the study baseline to the final value in each dose level will be provided. The ECG variables that will be analyzed are PR interval, QRS interval, and QT corrected with Fridericia's formula (QTcF). The actual value and change from study baseline of ECG measurements will be summarized by study part and visits. In addition, change from baseline to the last assessment of the final dose level will be summarized.

All-important abnormalities from the ECG readings that, in the opinion of the Investigator are deemed clinically significant should be reported as AEs and will be listed in the AE listing.

All ECG data will be listed by subject and time of measurement.

## **12.7 PHYSICAL EXAMINATION**

All physical examination data will be listed by subject and time of measurement.

**Statistical Analysis Plan**

Catalyst Biosciences, Inc. Protocol # MAA-201

**Version 2.0**

**Syneos Health #1009647**

## **13 INTERIM ANALYSES**

No interim analyses are conducted during the study.

**Statistical Analysis Plan**

Catalyst Biosciences, Inc. **Protocol # MAA-201**

**Version 2.0**

**Syneos Health #1009647**

## **14 CHANGE FROM ANALYSIS PLANNED IN PROTOCOL**

1. Protocol primary efficacy endpoint stated the Poisson analysis will be performed using StatXact 11. However, SAS 9.4 will be used for the exact analyses as specified in this SAP.

Statistical Analysis Plan

Catalyst Biosciences, Inc. Protocol # MAA-201

Version 2.0

Syneos Health #1009647

## 16 PROGRAMMING CONSIDERATIONS

### 15.1 GENERAL CONSIDERATIONS

- One SAS program can create several outputs. / A separate SAS program will be created for each output.
- One output file can contain several outputs. / Each output will be stored in a separate file.
- Output files will be delivered in Word format / pdf format.
- Numbering of TFLs will follow ICH E3 guidance

### 15.2 TABLE, LISTING, AND FIGURE FORMAT

#### 15.2.1 General

- All TLFs will be produced in landscape format, unless otherwise specified.
- All TLFs will be produced using the Courier New font, size 8
- The data displays for all TLFs will have a minimum 1-inch margin on all 4 sides.
- Headers and footers for figures will be in Courier New font, size 8.
- Legends will be used for all figures with more than 1 variable, group, or item displayed.
- TLFs will be in black and white (no color), unless otherwise specified
- Specialized text styles, such as bolding, italics, borders, shading, and superscripted and subscripted text, will not be used in the TLFs, unless otherwise specified. On some occasions, superscripts 1, 2, or 3 may be used (see below).
- Only standard keyboard characters will be used in the TLFs. Special characters, such as non-printable control characters, printer-specific, or font-specific characters, will not be used. Hexadecimal-derived characters will be used, where possible, if they are appropriate to help display math symbols (e.g.,  $\mu$ ). Certain subscripts and superscripts (e.g., cm^2, Cmax) will be employed on a case-by-case basis.
- Mixed case will be used for all titles, footnotes, column headers, and programmer-supplied formats, as appropriate.

#### 15.2.2 Headers

- All output should have the following header at the top left of each page:  
<Sponsor Name> Protocol XXX (Syneos Health study number xxx)
- All output should have Page n of N at the top or bottom right corner of each page. TLFs should be internally paginated in relation to the total length (i.e., the page number should appear sequentially as page n of N, where N is the total number of pages in the table).

**Statistical Analysis Plan**

Catalyst Biosciences, Inc. Protocol # MAA-201

Version 2.0

Syneos Health #1009647

- The date output was generated should appear along with the program name as a footer on each page.

### 15.2.3 Display Titles

- Each TLF should be identified by the designation and a numeral. (i.e., Table 14.1.1). ICH E3 numbering is strongly recommended but sponsor preferences should be obtained prior to final determination (see also template 03.007C “Table of Contents for Tables Listings and Figures in Statistical Analysis Plan”). A decimal system (x.y and x.y.z) should be used to identify TLFs with related contents. The title is centered. The analysis set should be identified on the line immediately following the title. The title and table designation are single spaced. A solid line spanning the margins will separate the display titles from the
- Column headers. There will be 1 blank line between the last title and the solid line.

Table x.y.z  
First Line of Title  
Second Line of Title if Needed  
(ITT Analysis Set)

### 15.2.4 Column Headers

- Column headings should be displayed immediately below the solid line described above in initial upper-case characters.
- In the case of efficacy tables, the variable (or characteristic) column will be on the far left followed by the treatment group columns and total column (if applicable). P-values may be presented under the total column or in separate p-value column (if applicable). Within-treatment comparisons may have p-values presented in a row beneath the summary statistics for that treatment.
- For numeric variables, include “unit” in column or row heading when appropriate.
- Analysis set sizes will be presented for each treatment group in the column heading as (N=xx) (or in the row headings if applicable). This is distinct from the ‘n’ used for the descriptive statistics representing the number of subjects in the analysis set.

### 15.2.5 Body of the Data Display

#### 15.2.5.1 General Conventions

Data in columns of a table or listing should be formatted as follows:

- alphanumeric values are left-justified;
- whole numbers (e.g., counts) are right-justified; and
- numbers containing fractional portions are decimal aligned.

Statistical Analysis Plan

Catalyst Biosciences, Inc. Protocol # MAA-201

Version 2.0

Syneos Health #1009647

### 15.2.5.2 Table Conventions

- Units will be included where available
- If the categories of a parameter are ordered, then all categories between the maximum and minimum category should be presented in the table, even if n=0 for all treatment groups in a given category that is between the minimum and maximum level for that parameter. For example, the frequency distribution for symptom severity would appear as:

Severity Rating	N
severe	0
moderate	8
mild	3

Where percentages are presented in these tables, zero percentages will not be presented and so any counts of 0 will be presented as 0 and not as 0 (0%).

- If the categories are not ordered (e.g., Medical History, Reasons for Discontinuation from the Study, etc.), then only those categories for which there is at least 1 subject represented in 1 or more groups should be included.
- An Unknown or Missing category should be added to any parameter for which information is not available for 1 or more subjects.
- Unless otherwise specified, the estimated mean and median for a set of values should be printed out to 1 more significant digit than the original values, and standard deviations should be printed out to 2 more significant digits than the original values. The minimum and maximum should report the same significant digits as the original values. For example, for systolic blood pressure:

N	XX
Mean	XXX.X
Std Dev	X.XX
Median	XXX.X
Minimum	XXX
Maximum	XXX

- P-values should be output in the format: “0.xxxx”, where xxxx is the value rounded to 4 decimal places. Any p-value less than 0.0001 will be presented as <0.0001. If the p-value is returned as >0.9999 then present as >0.9999
- Percentage values should be printed to one decimal place, in parentheses with no spaces, one space after the count (e.g., 7 (12.8%), 13 (5.4%)). Pre-determine how to display values that round down to 0.0. A common convention is to display as '<0.1', or as appropriate with additional decimal places. Unless otherwise noted, for all percentages, the number of subjects in the analysis set for the treatment group who have an observation will be the denominator. Percentages after zero counts should not be displayed and percentages equating to 100% should be presented as 100%, without any decimal places.

**Statistical Analysis Plan**

Catalyst Biosciences, Inc. Protocol # MAA-201

**Version 2.0**

**Syneos Health #1009647**

- Tabular display of data for medical history, prior / concomitant medications, and all tabular displays of adverse event data should be presented by the body system, treatment class, or SOC with the highest occurrence in the active treatment group in decreasing order, assuming all terms are coded. Within the body system, drug class and SOC, medical history (by preferred term), drugs (by ATC3 code), and adverse events (by preferred term) should be displayed in decreasing order. If incidence for more than 1 term is identical, they should then be sorted alphabetically.
- Where a category with a subheading (such as system organ class) has to be split over more than one page, output the subheading followed by “(cont)” at the top of each subsequent page. The overall summary statistics for the subheading should only be output on the first relevant page.

### 15.2.5.3 Listing Conventions

- Listings will be sorted for presentation in order of treatment groups as above, subject number, visit/collection day, and visit/collection time.
- Dates should be printed in SAS® DATE9.format (“ddMMMyyyy”: 01JUL2000). Missing portions of dates should be represented on subject listings as dashes (--JUL2000).
- All observed time values must be presented using a 24-hour clock HH:MM or HH:MM:SS format (e.g., 11:26:45, or 11:26). Time will only be reported if it was measured as part of the study.
- Units will be included where available

### 15.2.5.4 Figure Conventions

- Unless otherwise specified, for all figures, study visits will be displayed on the X-axis and endpoint (e.g., treatment mean change from Baseline) values will be displayed on the Y-axis.

### 15.2.6 Footnotes

- A solid line spanning the margins will separate the body of the data display from the footnotes.
- All footnotes will be left justified with single-line spacing immediately below the solid line underneath the data display.
- Footnotes should always begin with “Note:” if an informational footnote, or 1, 2, 3, etc. if a reference footnote. Each new footnote should start on a new line where possible.
- Subject specific footnotes should be avoided, where possible.

**Statistical Analysis Plan**

Catalyst Biosciences, Inc. Protocol # MAA-201

**Version 2.0**

**Syneos Health #1009647**

- Footnotes will be used sparingly and must add value to the table, figure, or data listing. If more than six lines of footnotes are planned, then a cover page may be used to display footnotes, and only those essential to comprehension of the data will be repeated on each page.
- The last line of the footnote section will be a standard source line that indicates the name of the program used to produce the data display, date the program was run, and the listing source.

**Statistical Analysis Plan**

Catalyst Biosciences, Inc. **Protocol # MAA-201**

**Version 2.0**

**Syneos Health #1009647**

## **17 QUALITY CONTROL**

SAS programs are developed to produce output such as analysis data sets, summary tables, data listings, figures or statistical analyses. Syneos Health SOP 03.010 and 03.013 provide an overview of the development of such SAS programs.

Syneos Health SOP 03.009 describes the quality control procedures that are performed for all SAS programs and output. Quality control is defined here as the operational techniques and activities undertaken to verify that the SAS programs produce the output by checking for their logic, efficiency and commenting and by review of the produced output.

SAS programming and quality control plan will be created.

**Statistical Analysis Plan**

Catalyst Biosciences, Inc. Protocol # MAA-201

**Version 2.0**

**Syneos Health #1009647**

## **APPENDIX I EXAMPLE SAS CODE**

**Poisson regression model for primary efficacy endpoint:**

```
PROC GENMOD DATA = bleed;  
MODEL abr = / DIST = poi LINK = log PRED OFFSET = <ln (12)>;  
EXACT intercept/ESTIMATE = parm ONESIDED ALPHA = 0.025;  
RUN;
```

**Poisson regression model for primary sensitivity analysis:**

```
PROC GENMOD DATA = bleed;  
CLASS subjid time  
MODEL abr = time / DIST = poi LINK = log PRED;  
REPEATED SUBJECT = subjid/ CORRW TYPE = un;  
LSMEANS time/DIFF CL;  
RUN;
```

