Dose interruption and surgery: Daily SC study injections will be interrupted, as needed, if there is a need for a surgical procedure; an event requiring extended (>48 hours) hospitalization; a thrombotic event; clinical evidence of inhibitor formation; or laboratory results suggesting an antibody may be developing.

Measurements:

MarZAA antigen and activity levels, as well as coagulation parameters, will be measured during Part 2 of the study at Day 1 (At pre-dose and Hour 7 post-dose, Day 3 (Pre-dose), Day 5 (Pre-dose), Day 7 (Pre-dose and Post-dose Hour 7).

MAA-201 VERSION 2.0

If no spontaneous bleeding occurs at the first dose level in part 2 of the study, trough antigen and activity, as well as coagulation parameters, will be measured on days 14, 21, 28, and 50 after starting their dosing regimen.

If spontaneous bleeding occurs after the fifth daily dose at any dose level, MarzAA antigen and activity levels will be measured within 6 hours of the spontaneous bleed (if feasible). Specimens for coagulation and immunogenicity testing will also be drawn.

Once it is determined to escalate to the next dose level, a pre-dose and Hour 7 post-dose specimen, will be drawn for PK, coagulation, and thrombogenicity markers on Day 7 *after* the dose has been escalated to estimate the *new* trough and peak concentrations (PCs) and PD. MarzAA antigen and activity levels, as well as coagulation parameters, will then be measured (pre-dose) at Day 14, 21, 28, and 50 after dose escalation.

Immunogenicity assays: Specimens for immunogenicity testing (antibody to MarzAA, neutralizing activity, cross reactivity) will be drawn at screening, Part 1a pre-dose, Part 1b pre-dose, and during part 2 pre-dose on Day 1, 7, 14, 21, 28, and 42, and then every two weeks until end of study.

Number of planned subjects: 12

Trial population:

Inclusion criteria:

1. Confirmed diagnosis of severe congenital hemophilia A or B with an inhibitor.
2. History of frequent spontaneous bleeding episodes (historical annualized bleeding rate [ABR] of ≥ 12).
3. Male, age 18 or older.
4. Agreement to use highly effective birth control throughout the study.
5. Affirmation of informed consent with signature confirmation before any trial-related activities. (Trial related activities are any procedure that would not have been performed during normal clinical management of the subject).
6. Stated willingness to comply with all study procedures and availability for the duration of the study.

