4.2 END OF STUDY DEFINITION

The minimum duration of treatment for each subject is approximately 2 months (if no dose escalation is required) and the maximum duration is approximately 7 months (if three dose escalations are required).

Up to 4 weeks for screening period; 24 hours for the part 1a (single IV dosing and PK/PD/Safety testing); 48 hours for the Part 1b (single SC dosing and PK/PD/safety testing); and up to 197 days of daily SC dosing and a PK/PD/safety follow-up assessment 30 days after last dose. Subjects must have no spontaneous bleeding for 50 days if on the first three dose levels or complete 50 days of treatment on the fourth dose level. The end of study visit will be 30 days after the last dose of study drug treatment in Part 2.

A participant is considered to have completed the study if he has completed all phases of the study, including treatment at the same dose level for 50 days, and returned for procedures listed under end of study visit as shown in the SOA.

MAA-201 VERSION 2.0

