## 4. ENDPOINTS

### 4.1 PRIMARY EFFICACY ENDPOINT

The primary efficacy endpoint is:

- ABR (spontaneous and total) during Part 2 when on final MarzAA dose level versus recorded historical ABR

Bleeding events will be evaluated as follows:

- Spontaneous versus traumatic/traumatic

A spontaneous bleeding episode is defined as one that is precipitated by normal ADL.

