## 8. EFFICACY

Efficacy analyses will be based on the ITT, modified ITT and per-protocol population and summarized by study part, final dose level and overall.

The primary efficacy endpoint will be tested inferentially using a one-sided test with 2.5% significance level. All other statistical tests will be performed at the 0.05 significance level using two-sided tests (i.e. two-sided 95% CIs).

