### 8.1 PRIMARY EFFICACY ENDPOINT AND ANALYSIS

#### 8.1.1 Primary Efficacy Endpoint

The analysis of the primary endpoint (annualized bleeding rate (ABR) for spontaneous and traumatic bleeds) under the final treated dose of MarzAA for each subject will be based on the one sample test compared to a pre-defined rate assumed for the on-demand therapy. The pre-defined rate is assumed to be 12 bleeds in total (i.e. one bleed per month), defined as the minimum ABR for each subject according to inclusion criterion 2 (defined as the null hypothesis (H0)). The comparison of the actual ABR for MarzAA at the highest dose for an individual will be performed using the one-sample test for a Poisson rate versus the pre-defined margin of 12 (using an exact Poisson regression model in SAS 9.4). A one-tailed 2.5% significance level will be used For the following hypothesis test:

$$H_0: ABR_{\text{MarzAA}} \geq 12 \text{ versus } H_1: ABR_{\text{MarzAA}} < 12.$$

The ITT population will be used for the statistical analysis of the primary efficacy endpoint.

In order to calculate the ABR for subjects who do not have a total of 12 months of follow up, the ABR will be calculated as:

$$(\text{Number of bleeds/number of months on study}) \times 12$$

Note: number of months is calculated as the exposure (in days) at each dose level / 30.5.

Formally, assume that the hypothesis is: H0:  $\lambda = \lambda_0$  vs Ha:  $\lambda < \lambda_0$ . Let n be the number of subjects, we can calculate the critical point Ncrit which is the largest integer meeting

$$\sum_0^{N_{crit}} e^{-n\lambda_0} \frac{(n\lambda_0)^k}{k!} \leq \alpha \quad (1)$$

If the total number of bleeds during the final MarzAA dose for all subjects is less than Ncrit, then the null hypothesis is rejected.

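### The ABR sensitivity GEE coded in SAP Appendix I rejects about 8–9% of the time at a nominal 5% with 12 subjects, and has no finite contrast when no bleed is counted at the final dose

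*SAP*

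**What the plan says.** SAP Appendix I gives example code under a label for the primary sensitivity analysis. The model is "MODEL abr = time / DIST = poi LINK = log PRED", with "REPEATED SUBJECT = subjid/ CORRW TYPE = un" and "LSMEANS time/DIFF CL". This is a GEE, so inference rests by default on sandwich standard errors and normal limits. No small-sample adjustment appears, and nothing covers a zero count.

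The body of the SAP does not describe this model. Section 8.1.2 only repeats the primary analysis in the modified ITT and per-protocol populations. For the comparison with recorded history, section 8.1.1 uses an intercept-only model with log 12 as offset. The levels of `time` are not stated. The natural reading is history versus final dose, because SAP 4.1 defines the endpoint as "ABR (spontaneous and total) during Part 2 when on final MarzAA dose level versus recorded historical ABR" and this is the only coded model that could compare the two within subject.

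Section 8 sets the level for tests other than the primary: "All other statistical tests will be performed at the 0.05 significance level using two-sided tests". The planned number of subjects is 12. Protocol 4.2 adds the completion rule: "Subjects must have no spontaneous bleeding for 50 days if on the first three dose levels".

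**The concern.** Sandwich standard errors are too small when there are few clusters, and here there are 12. An uncorrected normal-reference test then rejects too often and its intervals are too narrow. The SAP recognises small samples elsewhere: section 10.4 brings in Kenward-Roger for the PD models for that reason, and section 9.4 codes it for PK. The efficacy GEE has no counterpart.

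The second fault is the log link. If every final-dose ABR is zero, the fitted log mean runs to minus infinity and the on-treatment residuals vanish. For spontaneous ABR the design pushes towards that result. A subject who finishes on 30, 60 or 90 µg/kg can have a spontaneous bleed at that level only around the first five doses, since a later one triggers escalation. The model could therefore have no answer for the most favourable spontaneous-bleed result.

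**Working it through.** **The plan's own figure.** The only operating characteristic stated is the power of the primary one-sample Poisson test (SAP 3.5: ABR 12 versus 6, one-sided 2.5%). With one year per subject, the null mean for 12 subjects is 144. The critical count is 120 (tail probability 0.0227) and power is above 99.999%. For 6 subjects the null mean is 72, the critical count 55 and the power 99.88%. Both statements reproduce, but nothing is stated for the GEE.

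**Inputs.** n = 12 (Protocol synopsis). History is 180 days (SAP 8.2.1) and final-dose follow-up 50 days (Protocol 4.2). Escalation follows any spontaneous bleed after the fifth dose, over four levels (Protocol 6.1.2). Assumed: two levels of `time`, complete pairs, Poisson counts within subject, and a traumatic rate of 0.5–1 per year, since the documents give none.

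**1. What the model reduces to.** With y1 the historical ABR, y2 the final-dose ABR, and m1 and m2 their means:

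- estimate = ln(m2/m1)
- sandwich variance = (1/n²) Σ (y1/m1 − y2/m2)²

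The working correlation drops out. Independence, exchangeable and unstructured fits all matched these formulas.

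**2. Type I error.** The variance uses divisor n, so |z| > 1.96 is approximately |t| > 1.96 × √(11/12) = 1.877 on 11 df. The error is 2P(t₁₁ > 1.877) = 8.7%. Simulation with equal true rates of 12 or 18 per year, no dose selection and subject CV 0–0.5 gave 8.4–9.1%. Over rates of 6–36 per year it was 7.8–9.3%, rising to 11.4% with strong heterogeneity (gamma shape 1, CV 1). With an n/(n−1) variance and t on 11 df, the error at 12 or 18 per year was 4.7–5.3% for CV 0–0.5. With stronger heterogeneity (shape 2 to 1) it was 5.1–7.2%.

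**3. Chance of a zero count.** For spontaneous rate r per year, let a = exp(−5r/365) and q = exp(−45r/365). A subject settles at one of the first three levels with probability q each time, otherwise at the fourth, so P(no spontaneous bleed at final dose) = a × [1 − (1 − q)⁴]. Raise this to the power 12. For traumatic rate u, multiply by exp(−12 × 50u/365), which is 0.440 at u = 0.5 and 0.193 at u = 1.

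| r | a | q | per subject | all 12, spontaneous | total, u = 0.5 | total, u = 1 |
|---|---|---|---|---|---|---|
| 1 | 0.986 | 0.884 | 0.986 | 85% | 37% | 16% |
| 2 | 0.973 | 0.781 | 0.971 | 70% | 31% | 14% |
| 3 | 0.960 | 0.691 | 0.951 | 55% | 24% | 11% |
| 6 | 0.921 | 0.477 | 0.852 | 15% | 6% | 3% |

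The spontaneous column falls below 50% at about 3.3 per year. For total ABR 6 without escalation, the chance is exp(−12 × 6 × 50/365) = exp(−9.86), or 0.005%.

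**4. What software may print.** PROC GENMOD was not available. A GEE routine in another package, given all-zero final-dose data, returned −27.4 with standard error 0.30 and no warning. One bleed in one subject gave −3.49 with standard error 0.99.

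**5. An exact alternative at zero.** Suppose 90 historical bleeds in 12 × 180 days and none in 12 × 50 days. Conditional on the total, p = (180/230)⁹⁰ ≈ 3 × 10⁻¹⁰. The 97.5% upper limit R for the rate ratio solves (180/(180 + 50R))⁹⁰ = 0.025. So R = (180/50) × (0.025^(−1/90) − 1) = 0.15.

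**6. Dose selection.** Simulating an ineffective drug (12 spontaneous bleeds per year throughout, escalation rule applied, final level analysed), the coded GEE rejects about 40% of the time. The exact conditional test at one-sided 2.5% rejects about 53%. Without selection the exact test's error is 1.8%.

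**The case against.** The strongest reply is that this is example code for a supporting model that section 8.1 never describes. The decision rests on an exact one-sample test, for which zero bleeds is the clearest possible rejection. That stands, and it limits the reach of the point. It does not clear the code, which is labelled the primary sensitivity analysis and would be run as printed.

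Four stronger readings are tempting and not supported:

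- **A zero count is likely whenever the drug works.** The planning value is an ABR of 6 or less. At 6 the chance is 15% for spontaneous bleeds and 0.005% for total bleeds without escalation. Zero is the likelier outcome only for spontaneous ABR at about 3 per year or less.
- **The program will fail to run.** This was not verified in PROC GENMOD. Another routine ran and printed a meaningless estimate, which may be worse because it can pass unnoticed.
- **The unstructured correlation is to blame.** With two complete time levels it changes neither the estimate nor the standard error. The causes are the log link and the uncorrected sandwich test.
- **An exact conditional test would hold its level.** It does not for final-dose spontaneous ABR (step 6). It also assumes Poisson variation within subject: with no selection but an assumed period-to-period CV of 0.5 or 0.7, its simulated one-sided error is 5.0% or 8.2%.

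It is also fair that 8–9% is not the largest error here. For spontaneous ABR, selection of the final dose is larger. That is a separate problem, and the changes below do not cure it.

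**Conclusion.** The point holds in limited form. Read as history versus final dose with 12 complete pairs, the coded GEE rejects about 8–9% of the time at a nominal two-sided 5%, even without dose selection. It has no finite contrast or valid interval when no counted bleed occurs at the final dose. How often that happens depends on the unknown true rates: more often than not for spontaneous ABR at about 3 per year or less, about 11–37% for total ABR over the range tabulated at 1–3 spontaneous bleeds per year, and negligible for total ABR at 6 without escalation. These figures rest on the assumed meaning of `time`, Poisson counts within subject and the assumed traumatic rates. The primary exact test is untouched by these two faults. The change is worth making before database lock, but it concerns a supporting analysis.

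**What to change.** 1. Define `time` as history versus Part 2, state the history window and the days counted in each period, and describe the model in section 8.1.2.
2. If the GEE is kept, apply a small-sample variance correction such as n/(n−1), with t limits on n−1 degrees of freedom.
3. When the on-treatment count is zero, report the upper limit from a subject-stratified exact conditional Poisson comparison (bleed counts as response, log days as offset, subject as stratum) in place of the GEE contrast. State that it assumes Poisson variation within subject. The SAP's primary code already uses the EXACT statement.
4. State that neither method corrects the bias from analysing only the final dose chosen by escalation, and do not describe the exact test as holding its level for final-dose spontaneous ABR.

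The cost is a few lines of code and text. On the log scale the GEE intervals widen by √(12/11) × 2.201/1.960 = 1.17, or about 17%. The exact test is slightly conservative when there is no selection. No data collection changes.
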